## 12.7.2 Adverse Events of Special Interest

An AESI is a noteworthy treatment-emergent event for the study drug that should be monitored closely and reported promptly. See Section 12.7.5 for reporting procedure(s). An AESI can be either serious or nonserious.

Based on the potential risks of nemolizumab and the risks associated with biologics (and their biosimilar equivalents) in general (i.e., class effects), the following AEs will be considered AESIs:

- Injection-related reactions
  - Anaphylactic reactions
  - Acute allergic reactions requiring treatment
  - Severe injection site reaction (i.e., lasting >24 hours)
- Newly-diagnosed asthma or worsening of asthma
  - More specifically, subjects *with* a medical history of asthma will be referred to the physician who manages their asthma when:
    - ACT score  $\leq 19$ : An ACT score  $\leq 19$  conveys asthma that may not be adequately controlled. An AESI is reported based on the Investigator's clinical judgment, including consideration of the managing physician's report.
    - PEF  $<80\%$  of the predicted value: An AESI is to be reported based on the investigator's clinical judgment, including consideration of the managing physician's report.
    - Unexpected worsening of asthma is observed or reported. An AESI is reported based on the Investigator's clinical judgment.
  - Subjects *without* a medical history of asthma will be referred to an appropriate respiratory physician/specialist when:
    - Signs and/or symptoms suggestive of asthma have been observed or reported. An AESI is reported based on the Investigator's clinical judgment of the specialist's report.
    - Respiratory assessments (i.e., examination, PEF) suggest a decline in the subject's respiratory health. An AESI is reported based on the Investigator's clinical judgment of the specialist's report.
- Infections
  - Any severe infection or any infection requiring treatment with parenteral antibiotics or oral antibiotics/antivirals/antifungals for  $>2$  weeks
  - Any confirmed or suspected COVID-19 infection (Section 8.3.2)
- Peripheral edema: limbs, bilateral
- Facial edema
- Elevated ALT or AST ( $>3 \times$  ULN) in combination with elevated bilirubin ( $>2 \times$  ULN)

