13.2.1. Clinical Laboratory Evaluations

The hematology laboratory analyses, clinical chemistry laboratory analyses, and urinalyses will be performed at a central laboratory. Reference ranges will be supplied by the central laboratory and used by the investigator to assess the laboratory data for clinical significance and pathological changes. Reference ranges will be provided in the laboratory manual.

The following parameters will be reported for laboratory data.

- **Hematology:** Hemoglobin, hematocrit, white blood cell (WBC) count (with differential including eosinophils), red blood cell (RBC) count, platelet count, and mean cell volume (MCV).
- **Chemistry:** Creatinine, aspartate aminotransferase (AST), alanine aminotransferase (ALT), gamma glutamyl transferase, alkaline phosphatase, lactate dehydrogenase, total bilirubin, direct bilirubin, albumin, total protein, uric acid, sodium, potassium, calcium, chloride, glucose, urea, total cholesterol, triglycerides, low-density lipoprotein, high-density lipoprotein, creatine phosphokinase (CPK). CPK isoenzyme test will be performed only if CPK is elevated to $>2.5 \times$ upper limit of normal (ULN).
- **Urinalysis:** pH, glucose, ketones, blood, protein, leukocytes, nitrites, bilirubin, urobilinogen, and specific gravity.

Laboratory assessments are performed at Baseline/Day 1, Week 12, Week 24, Early Termination and Week 32/Follow-up.

Hematology and chemistry laboratory data (absolute values and change from Baseline) will be summarized as continuous variables by visit (Baseline and scheduled visits only). Urinalysis laboratory data will be summarized by visit (Baseline and scheduled visits only). Last post-baseline, worst post-baseline and maximum post-baseline results will also be included in the summaries and will include unscheduled visits

This document is confidential.

in the derivation. Worst post-baseline value will be defined as the highest or lowest value relative to the reference range. Parameters will be presented in alphabetically order.

Shift tables will be generated using the reference ranges (Low, Normal, High and Missing) for hematology and chemistry laboratory data. The number and percentage of subjects shifting from reference ranges between Baseline and each visit (scheduled visits only) will be summarized. Last, worst and maximum post baseline values will also be included in the shift tables and will include unscheduled visits in the derivation.

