Summary of the number and percentage of subjects who met criteria of potential clinically significant (CS) value will be summarized (scheduled visits only) for hematology, chemistry. Last, worst and maximum post-baseline results will also be included in the summaries. Potentially CS ranges are listed in [Section 20.2](#).

For statistical and graphical summaries of the laboratory tests, values below or above the limit of detection (e.g. '< 3' or '> 500') are substituted with the lower limit of detection minus 1% for values below the lower limit and are substituted with the upper limit of detection plus 1% for values above the upper limit (e.g. '< 3' is substituted by '2.97', '> 500' is substituted by '505'). In data listings, the values are shown including the < or > sign.

Distribution of continuous hematology and chemistry laboratory data (in particular, Aspartate Aminotransferase (AST), Alanine Aminotransferase (ALT), Alkaline Phosphatase (ALP), Total Bilirubin (BILI), Creatinine Kinase (CK) and Leukocytes (WBC)) will be displayed graphically as boxplot by treatment group for baseline and for each scheduled visits and the maximum post-Baseline (including unscheduled visits in the derivation) values.

By-subject listing will be presented for all laboratory data. By-subject listing for subjects with at least one abnormal result (out of reference range) will be provided for hematology and clinical chemistry. By-subject listing for subjects with at least one potentially CS result will be provided for hematology, clinical chemistry.

All laboratory data will be listed for the Safety population.

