14.3.4.1.2		Blood Chemistry Data	
	14.3.4.1.2.1	Summary of Laboratory Data for Clinical Chemistry	Safety Population

This document is confidential.

Header	Table Number	Name	Analysis Set
	14.3.4.1.2.2	Shift from Baseline for Clinical Chemistry by Reference Range	Safety Population
	14.3.4.1.2.3	Summary of Potentially Clinically Significant Clinical Chemistry	Safety Population
	14.3.4.1.2.4	Listing of Subjects with Abnormal Clinical Chemistry Results	Safety Population
	14.3.4.1.2.5	Listing of Subjects with Potentially Clinically Significant Clinical Chemistry Results	Safety Population
14.3.4.1.3		Urinalysis Data	
	14.3.4.1.3.1	Summary of Laboratory Data for Urinalysis	Safety Population
14.3.4.1.4		Pregnancy Test	
	14.3.4.1.4.1	Summary of Pregnancy Test Results by Visit	Safety Population
14.3.4.2		Vital Signs	
	14.3.4.2.1	Summary of Vital Signs, Height and Weight	Safety Population
	14.3.4.2.2	Proportions of Subjects with Potentially Clinically Significant Vital Signs and Weight	Safety Population
	14.3.4.2.3	Listing of Subjects with Potentially Clinically Significant Vital Signs and Weight	Safety Population
14.3.4.3		Electrocardiogram (ECG) Data	
	14.3.4.3.1	Summary of Observed Values and Changes from Baseline for Electrocardiogram (ECG) Parameters by Visit	Safety Population
	14.3.4.3.2	Summary of Electrocardiogram (ECG)	Safety Population
	14.3.4.3.3	Summary of Electrocardiogram (ECG) Findings by Visit	Safety Population
14.3.4.4		Other Safety	
	14.3.4.4.1	Summary of Physical Examination	Safety Population
	14.3.4.4.2	Shift from Baseline in Physical Examination	Safety Population
	14.3.4.4.3	Listing of Subjects with Abnormal Results in Physical Examination	Safety Population
	14.3.4.4.4	Summary of Respiratory Assessments – Peak Expiratory Flow (PEF)	Safety Population
	14.3.4.4.5	Summary of Respiratory Assessments – Peak Expiratory Flow (PEF) for Subjects with Asthma History	Safety Population

This document is confidential.

Header	Table Number	Name	Analysis Set
	14.3.4.4.6	Summary of Respiratory Assessments – Peak Expiratory Flow (PEF) for Subjects without Asthma History	Safety Population
	14.3.4.4.7	Summary of Peak Expiratory Flow (PEF) < 80% of Predicted Value	Safety Population
	14.3.4.4.8	Summary of Peak Expiratory Flow (PEF) < 80% of Predicted Value for Subjects with Asthma History	Safety Population
	14.3.4.4.9	Summary of Peak Expiratory Flow (PEF) < 80% of Predicted Value for Subjects without Asthma History	Safety Population

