Potentially clinically significant ranges for Blood Chemistry parameters are defined in [Table 20-2](#) Potentially Clinically Significant Ranges for Blood Chemistry Parameters.

Table 20-2 Potentially Clinically Significant Ranges for Blood Chemistry Parameters

Test Parameter	Test Parameter Code	Normal Range Lower Limit (LLN)	Normal Range Upper Limit (ULN)	Potentially Clinically Significant Ranges
Aspartate Aminotransferase (U/L)	AST	8.00	40.00	> 3 x ULN at post-baseline, if baseline value \leq 3 x ULN
Alkaline Phosphatase (U/L)	ALP	55 (< 19 years old, Male) 45 (< 19 years old, Female) 40 (\geq 19 years old, Male) 35 (\geq 19 years old, Female)	149 (< 19 years old, Male) 87 (< 19 years old, Female) 129 (\geq 19 years old, Male) 104 (\geq 19 years old, Female)	> 2.5 x ULN at post-baseline, if baseline value \leq 2.5 x ULN
Alanine Aminotransferase (U/L)	ALT	5 (Male) 4 (Female)	48 (Male) 43 (Female)	> 3 x ULN at post-baseline, if baseline value \leq 3 x ULN
Bilirubin (umol/L)	BILI	3.00	21.00	> 1.5 x ULN at post-baseline, if baseline value \leq 1.5 * ULN
Calcium (mmol/L)	CA	2.07	2.64	< 2 at post-baseline, if baseline value \geq 2
Chloride (mmol/L)	CL	94.00	112.00	> 2.9 at post-baseline, if baseline value \leq 2.9 < 94 at post-baseline, if baseline value \geq 94 > 115 at post-baseline, if baseline value \leq 115
Cholesterol (mmol/L)	CHOL	2.95 (< 20 years old, Male)	5.12 (< 20 years old, Male)	> 7.75 at post-baseline, if baseline value \leq 7.75 (Female \leq 60 years old, Male \leq 70 years old); > 8.28 at post-baseline, if baseline value \leq 8.28 (Female $<$ 60 - 70 years old); > 7.76 at post-baseline, if baseline value \leq 7.76 (Male $>$ 70 years old); > 9.10 at post-baseline, if baseline value \leq 9.10 (Female $>$ 70 years old)
		3.23 (< 20 years old, Female)	5.48 (< 20 years old, Female)	

This document is confidential.

Test Parameter	Test Parameter Code	Normal Range Lower Limit (LLN)	Normal Range Upper Limit (ULN)	Potentially Clinically Significant Ranges
		3.31 (20 - < 30 years old, Male)	6.10 (20 - < 30 years old, Male)	
		3.31 (20 - < 30 years old, Female)	5.64 (20 - < 30 years old, Female)	
		3.88 (30 - < 40 years old, Male)	6.83 (30 - < 40 years old, Male)	
		3.65 (30 - < 40 years old, Female)	6.21 (30 - < 40 years old, Female)	
		4.19 (40 - < 50 years old, Male)	7.24 (40 - < 50 years old, Male)	
		4.01 (40 - < 50 years old, Female)	6.85 (40 - < 50 years old, Female)	
		4.40 (50 - < 60 years old, Male)	7.53 (50 - < 60 years old, Male)	

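### The liver adverse event of special interest is a joint laboratory rule, but the SAP tabulates it only from investigator reports, and its separate laboratory flags do not give the joint count

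*SAP*

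**What the plan says.** Protocol 12.7.2 and SAP 13.1 give the same liver AESI: ALT or AST above 3xULN "in combination with elevated bilirubin" above 2xULN. Neither says how close in time the two elevations must be. Both describe an AESI as a treatment-emergent event. The AESI tables (14.3.1.16, .17, .26 and .27 in the SAP's Index of Tables) are TEAE tables by category, SOC and preferred term. They are fed by what investigators report under Protocol 12.7.5.

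For the laboratory data, SAP 13.2.1 states: "Summary of the number and percentage of subjects who met criteria of potential clinically significant (CS) value will be summarized (scheduled visits only", for hematology and chemistry. It continues: "Last, worst and maximum post-baseline results will also be included in the summaries". The ranges are in SAP 20.2, Table 20-2:

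- AST and ALT, in separate rows: "> 3 x ULN at post-baseline, if baseline value" is at or below 3xULN.
- Bilirubin: "> 1.5 x ULN at post-baseline, if baseline value" is at or below 1.5xULN.

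The output is Table 14.3.4.1.2.3, "Summary of Potentially Clinically Significant Clinical Chemistry". The other categorical chemistry output is cruder: "Shift tables will be generated using the reference ranges (Low, Normal, High and Missing) for hematology and chemistry laboratory data". No indexed chemistry table or figure (14.3.4.1.2.1 to .6) combines a transaminase with bilirubin or cuts bilirubin at 2xULN.

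**The concern.** AESI incidence is a named safety endpoint, and safety against placebo is the secondary objective. The liver AESI is the one listed AESI that is stated wholly as laboratory values, so it can be derived without judgment. Under the plan it is nevertheless counted only if an investigator files it, and Protocol 12.5 makes AE reporting of a laboratory value depend on the investigator judging it clinically significant.

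If a subject met the joint rule and no report was filed, the AESI tables would show nothing, and the laboratory table would show at most unconnected single-test flags. If no subject met it, the report could not state that zero from a planned joint tabulation.

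The SAP treats another AESI differently. For asthma it tabulates the objective triggers from the data (PEF below 80% of predicted in 13.6.3, ACT of 19 or less in 13.6.1) alongside the reported events.

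**Working it through.** There is no sample-size or power figure to reproduce. The check compares the two sets of definitions and asks whether the planned flag counts fix the joint count.

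**Inputs (SAP Table 20-2).** ULNs: AST 40 U/L; ALT 48 U/L (male) and 43 U/L (female); bilirubin 21 umol/L.

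**Cut-offs in units.**

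- AST: 3 x 40 = 120 U/L.
- ALT: 3 x 48 = 144 U/L (male); 3 x 43 = 129 U/L (female).
- Bilirubin flag: 1.5 x 21 = 31.5 umol/L. Bilirubin in the AESI: 2 x 21 = 42 umol/L.

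The transaminase cut is the same in both. The bilirubin flag also takes in values above 31.5 and up to 42, which cannot be part of the AESI. Each flag drops subjects whose baseline already exceeds that flag's own cut; the AESI has no such per-test condition.

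**Do the counts fix the joint event?** Take four hypothetical arms of 20, with values in multiples of ULN, one transaminase for simplicity, and baselines of 0.5 unless stated. A subject is flagged for transaminase if >3 with baseline <=3, flagged for bilirubin if >1.5 with baseline <=1.5, and joint if transaminase >3 and bilirubin >2.

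| Arm | Subjects with elevations | Transaminase flags | Bilirubin flags | Joint cases | Highest bilirubin (umol/L) |
|---|---|---|---|---|---|
| A | 2 with transaminase 4 and bilirubin 2.5 | 2 | 2 | 2 | 2.5 x 21 = 52.5 |
| B | 2 with transaminase 4; 2 others with bilirubin 2.5 | 2 | 2 | 0 | 52.5 |
| C | 2 with transaminase 4 and bilirubin 1.8 | 2 | 2 | 0 | 1.8 x 21 = 37.8 |
| D | 1 with transaminase 4 and bilirubin 2.5, baseline bilirubin 1.6 | 1 | 0 | 1 | 52.5 |

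Arms A, B and C are identical in the flag table but hold 2, 0 and 0 joint cases. In arm D the joint rule is met although the bilirubin count is 0, because the baseline of 1.6 x 21 = 33.6 exceeds 31.5. The bilirubin count is therefore not even an upper limit for the joint count. The transaminase count would be one, unless transaminases already exceeded 3xULN at baseline.

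**What the other outputs add.** SAP 13.2.1 also summarizes chemistry as continuous variables, including the maximum post-baseline result with unscheduled visits, and SAP 8.1 reports the maximum of each variable. An arm whose highest bilirubin is 42 or less has no joint case in those data. That settles arm C. In arms A, B and D it shows that someone exceeded 42, and the by-subject listings must then be read.

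**Unscheduled samples.** For the continuous summaries and shift tables, SAP 13.2.1 says that unscheduled visits enter the last, worst and maximum values. It does not repeat this for the flag table.

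**The case against.** The strongest reply is that the laboratory outputs already allow a check. The maximum post-baseline bilirubin can exclude a case. The SAP also plans boxplots of AST, ALT and bilirubin with maximum values, and by-subject listings of all results, of abnormal results and of flagged results (16.2.8.1.2, 14.3.4.1.2.4 and 14.3.4.1.2.5). With about 40 subjects these can be read by hand. Investigators must evaluate every out-of-range value and report AESIs regardless of relatedness, and the IDMC monitors the listed AESIs. The table index is described as tentative.

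Much of this stands, and it rules out several stronger readings that a reader might infer:

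- That the laboratory outputs can neither confirm nor contradict the AESI count, or that the flagged-subject listing is the only place to find a case. The maximum and the fuller listings show otherwise.
- That the 1.5xULN cut misses cases. It is lower than 2xULN, so it over-includes; a bilirubin flag is lost only through the baseline condition. Even then, as in arm D, the transaminase flag still brings the subject into the flagged listing.
- That the flag table ignores everything outside scheduled visits. The sentence that follows adds last, worst and maximum results; only the source of those values is left unstated.
- That one case would settle the drug's liver safety. The documents do not say so, and Protocol 5.3 does not list liver injury among the important potential risks.

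The reply does not supply a count by arm of subjects who met the joint rule, or a stated comparison of that count with the reported AESIs. Such a comparison may exist in the IDMC charter or the data management plan, which are not part of these documents.

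**Conclusion.** The point holds as a gap in tabulation and reconciliation, not as a loss of data. A numeric joint criterion is counted only through investigator reports, and the separate flag counts do not determine it.

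The size is small. The event is likely to be absent in about 40 subjects, and no efficacy estimate, test or stated threshold is affected. The benefit is that the report could state a zero, or a case, from the laboratory data by arm.

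This rests on three assumptions: that Table 20-2's limits are the ones applied, that the index shows all planned chemistry outputs, and that no equivalent check sits in documents not seen here. The hypothetical arms show what is possible, not how often it would happen.

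**What to change.** Add two rows by arm to Table 14.3.4.1.2.3, and one reconciliation step:

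1. Subjects meeting the SAP's own joint AESI criterion after first dose. Apply treatment emergence to the joint event, not to each test. Include unscheduled samples and any local laboratory results, which Protocol Appendix 1 allows in exceptional situations. The sponsor should state the time window within which the two elevations count as combined, since the documents give none and each test's maximum may come from a different date.
2. Subjects with post-baseline bilirubin above 2xULN.
3. Before database lock, compare the derived cases with the reported liver AESIs and resolve any difference.

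No AESI threshold, flag range or clinical rule changes. The cost is one derivation, two table rows and a short reconciliation, almost entirely from data already collected. The downside is a row that will probably read zero.

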13.2.2. Pregnancy Testing

All women of childbearing potential will have a serum pregnancy test at the baseline visit and urine pregnancy tests (UPTs) at Baseline, Week 4, Week 8, Week 12, Week 16, Week 20 and Week 24, Early Termination visit, and Week 32/Follow-up. Pregnancy test results must be available prior to the administration of the study drug.

All confirmed pregnancy test results, premenses status and childbearing potential assessment results will be listed on the Safety population.

This document is confidential.

13.2.3. Virology and TB Testing

Virology including hepatitis B surface antigen (HBsAg), hepatitis B core antibody (HBcAb), hepatitis C virus (HCV), human immunodeficiency virus 1, and human immunodeficiency virus 2 antibodies may be assessed at unscheduled visits for safety purposes based on Investigator judgment. Subjects with a positive HBcAb and a negative HBsAg will also be assessed for hepatitis B surface antibody. Subjects with positive HCV antibodies will have a confirmatory test for HCV (e.g., PCR). All virology results will be listed on the Safety population.

Subjects may be assessed for active or latent tuberculosis (TB) at unscheduled visits for safety purposes based on Investigator judgment. A subject who tests positive for latent TB (with a positive QuantiFERON-TB Gold test) should be referred to the subject's treating physician for appropriate follow-up. All TB test results will be listed on the Safety population.

13.3. Vital Signs

Vital signs will include pulse rate, systolic and diastolic blood pressure (after the subject has been sitting for at least 5 minutes) and body temperature.

Vital signs will be collected at the at Baseline/Day 1, Week 4, Week 8, Week 12, Week 16, Week 20, and Week 24, Early Termination visit, and at Week 32/Follow-up.

Height and weight will be measured at Baseline for all subjects. Weight assessments will be conducted at Baseline/Day 1, and Week 24 and Early Termination.

All vital signs including height and weight (absolute values and change from Baseline) will be summarized as continuous (Baseline and scheduled visits only). Last post-Baseline results (including unscheduled visits in the derivation) will also be included.

The number and percentage of subjects who met criteria of potential CS value ([Section 20.2](#)) for vital signs and weight will be summarized (Baseline and scheduled visits only). Last post-Baseline results (including unscheduled visits in the derivation) will also be included.

Distribution of pulse rate, systolic and diastolic blood pressure will be displayed graphically as boxplot by treatment group for Baseline and each scheduled visit and maximum post-Baseline (including unscheduled visits in the derivation) values.

By-subject listing of subjects with potentially CS vital signs and weight will be provided.

All vital signs results will be listed on the Safety population.

This document is confidential.

13.4. ECG

A 12-lead electrocardiogram (ECG) will be performed and read centrally at Baseline/Day 1, Week 24 and Early Termination visit.

All ECG data (absolute values and change from Baseline) will be summarized as continuous variables by visit (Baseline and scheduled visits only). All parameters will be presented in alphabetically order.

The overall results of the ECGs recorded as 'Normal', 'Abnormal, NCS' or 'Abnormal, CS' will be summarized by treatment group and visit (scheduled visit only). Clinical significance will be determined by the investigator.

Additionally, all ECG findings will be summarized with numbers and percentages by visit (Baseline and scheduled visits only).

All ECG results will be listed on the Safety population.

13.5. Physical Examination

Following body system assessments will be performed at Baseline/Day 1, Week 12, Week 24, Early Termination, and Week 32/Follow-up:

- Head, ears, eyes, nose, throat, neck (including thyroid),
- Skin/integumentary system (excluding PN),
- Cardiovascular system,
- Respiratory system,
- Gastrointestinal system,
- Musculoskeletal system,
- Lymph nodes,
- Nervous system, and
- Extremities.

The number and percentage of subjects with physical examination results by body system classified as 'Normal', 'Abnormal, NCS' or 'Abnormal, CS' will be summarized (Baseline and scheduled visits only).

Shift from Baseline of the physical examination category will also be summarized by body system.

This document is confidential.

By-subject listing will be provided for subjects who have at least one abnormal result from any body system or who missed the assessment due to any reason.

All physical examination results will be listed on the Safety population.

